## Purpose of the Study

The trial is designed to provide the empirical data to compare the efficacy and safety of the invisa-RED Technology Elite Low-level Laser Therapy (LLLT) device with a sham device when used in the treatment of individuals for weight loss and aesthetics. At the conclusion of the trial; the change in body fat percentage, and the weight and inches lost of the two groups will be statistically analyzed to determine the efficacy of the invisa-RED Technology Elite in weight loss and/or aesthetics therapy.

### Background

"An estimated 160 million Americans are either obese or overweight. Nearly threequarters of American men and more than 60% of women are obese or overweight. These are also major challenges for America's children – nearly 30% of boys and girls under age 20 are either obese or overweight, up from 19% in 1980. Health risks such as cardiovascular disease, cancer, diabetes, osteoarthritis, and chronic kidney disease increase when a person's BMI exceeds 23. In 2010, obesity and overweight were estimated to have caused 3.4 million deaths globally, most of which were from cardiovascular causes. Research indicates that if left unaddressed, the rise in obesity could lead to future declines in life expectancy in countries worldwide." Christopher J.L. Murray *Professor, IHME Director, Chair, Department of Health Metrics Sciences* 

The invisa-RED Technology Elite device has been developed to assist in weight loss therapy that counters these trends.

## **Criteria for Participants**

The number of participants is projected to be forty (40).

There will be an equitable distribution of male and female participants.

Women who are pregnant, trying to get pregnant, or nursing will be excluded from the study, as they should not receive Low-level Laser Therapy (LLLT). There is no evidence of harm to a an unborn baby however there have been no safety tests either, so for medical legal reasons we recommend never treating such individuals.

The participants will be between the ages of 18-65 years.

The ethnicity of the participants will be equitably distributed.

Inclusion criteria will be individuals that may benefit from a weight loss therapy.

## Exclusion criteria will include the following:

- If you are pregnant, trying to get pregnant or nursing laser light therapy should be received only after the end of these conditions. There is no evidence of harm to a an unborn baby however there have been no safety tests either, so for medical legal reasons we recommend never treating areas directly over a developing child.
- Individuals with hypertension, light sensitive epilepsy, cancer, heart disease, infectious skin disease, and severe varicose veins should not use this device.
- People suffering from infectious and acute disease such as a fever should not use this device.
- People who have hemorrhagic disease, vascular ruptures, skin inflammation, or any disease of the skin should not use this device.
- People who have immune system dysfunction such as Leukemia, Hemophilia, etc., and light sensitive persons should not use this device.
- Individuals with a history of melanoma, raised moles, suspicious lesions, keloid scar formation, or healing problems should not undergo laser light therapy.
- Individuals with active infections, open lesions, hives, herpetic lesions, cold sores, or tattoos and permanent make-up in the area of treatment should not undergo laser light therapy.
- People who have used isotretinoin (commonly known as Accutane), tetracycline, St. John's Wort, or any photo sensitizing drugs in the last year should not undergo laser light therapy.
- Individuals with autoimmune diseases such as Lupus, Scleroderma, or Vitiligo should not undergo laser light therapy.
- Individuals who have pacemakers or other electro-stimulation devices surgically implanted should not undergo laser light therapy.
- Any insulin dependent individual should consult their physician before undergoing laser light therapy.
- All individuals considered "vulnerable" such as children, pregnant women, nursing home residents or other institutionalized persons, students, employees, fetuses, prisoners, and persons with decisional incapacity.

#### **Methods and Procedures**

The trial is designed to prove the efficacy and safety of the invisa-RED Technology Elite Low-level Laser Therapy (LLLT) device. The trial will compare results between two groups; the first will be treated using a fully functional invisa-RED Technology Elite device; this group will be internally designated the Usual Care Group. The second, a control group, will be treated utilizing a nonfunctional invisa-RED Technology Elite device; this group will be referred to internally as the Sham Group.

The sham device will consist of an invisa-RED Technology Elite device that will appear to operate as the Usual Care Group device to the operator, but the laser diodes will be disabled and will receive no power. If staff or a participant questions the efficacy of the sham device, an assertion may be made that only a near infrared, nonvisible frequency of light, is being employed.

The trial will be conducted employing a double blind study methodology; participants will be randomly assigned to each group through a drawing, neither participants nor clinicians will know to which trial group they are assigned. To ensure the double blind; treatment for the two groups will occur on separate days of the week. All participants will receive therapy at the [name] Chiropractic Center located in Hixson, TN. Group 1 will be assigned Monday, Wednesday, Friday, and Group 2; Tuesday, Thursday, and Saturday. Additionally staff administering the trial therapy will be assigned to work with one (1) group exclusively.

A simplified weight loss protocol will be employed based on the "Consultation Protocol" from the invisa-Red Training Manual. All study participants will undergo nine (9) therapy sessions of 20 minutes each; using a singular protocol setting for pulse (3.5s) and delay (0.2s), but power settings will be based on the participants Fitzpatrick Scale skin type. For skin types i and ii a power setting of 7 will be used, for skin types iii and iv a power setting of 6, for skin types v and vi a power setting of 4 will be employed. At the conclusion of the nine (9) therapy sessions; the change in body fat percentage, weight, and inches lost of the two groups will be statistically analyzed to determine the efficacy of the invisa-RED Technology Elite as a weight loss therapy. Any medical errors will be included in the statistical analysis.

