### **Data Analysis and Data Monitoring**

The measured weight loss and total inches lost per participant from the two groups will be statistically evaluated using an Independent T-Test with a P value of .05.

The study is classified as a minimal risk trial of short duration therefore a detailed plan for monitoring the data for participant safety is not required.

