## Data Storage and Security

All individuals participating in the trial will be assigned a participant number. Subsequently all clinical records and reports will reference only the participant number, ensuring that participants remain anonymous. Because of the low number of trial participants, only paper records will be maintained for all clinical and personal data. Records will be kept in locked storage and physical access will only be on a need to know basis. A participants' personal data correlating the participating individuals name and the trial participants Identifying Number will only be available to the principal investigator and trial administrator. All analytics will be performed using only data masked or redacted of any personal information.

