Statistical Analysis Plan

Cover Page

for the Clinical Study

"Comparing the Efficacy of a Dual-Frequency Laser-Emitting Device, the "invisared-RED Elite", With a Sham Device as Therapy for the Loss of Adipose Tissue (Body Fat) and Aesthetics in Overweight Individuals"

NCT03811093

May 7, 2019

Statistical Analysis Plan

for

Invisa-RED Clinical Trial

Research Questions:

Research Question One (1): Is there a statistically significant difference in Percentage of Body Fat Lost when using an invisa-RED Technology Elite Low-level Laser Therapy (LLLT) device when compared with a sham (placebo) device in an approved and standardized clinical protocol?

Null Hypothesis One (1): There is not a statistically significant difference in Percentage of Body Fat Lost when using an invisa-RED Technology Elite Low-level Laser Therapy (LLLT) device when compared with a sham (placebo) device as a therapy in an approved and standardized clinical protocol.

Alternative Hypothesis One (1): There is a statistically significant difference in Percentage of Body Fat Lost when using an invisa-RED Technology Elite Low-level Laser Therapy (LLLT) device when compared with a sham (placebo) device as a therapy in an approved and standardized clinical protocol.

Research Question Two (2): Is there a statistically significant difference in Inches Lost when using an invisa-RED Technology Elite Low-level Laser Therapy (LLLT) device when compared with a sham (placebo) device in an approved and standardized clinical protocol?

Null Hypothesis Two (2): There is not a statistically significant difference in Inches Lost when using an invisa-RED Technology Elite Low-level Laser Therapy (LLLT) device when compared with a sham (placebo) device in an approved and standardized clinical protocol.

Alternative Hypothesis Two (2): There is a statistically significant difference in Inches Lost when using an invisa-RED Technology Elite Low-level Laser Therapy (LLLT) device when compared with a sham (placebo) device in an approved and standardized clinical protocol.

Research Question Three(3): Is there a statistically significant difference in Pounds of Body Fat Lost when using an invisa-RED Technology Elite Low-level Laser Therapy (LLLT) device as a therapy when compared with a sham (placebo) device in an approved and standardized clinical protocol?

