An independent samples *t*-test is the appropriate statistical test when the purpose of research is to assess if differences exist on a continuous (interval/ratio) dependent variable by a dichotomous (2 groups) independent variable. The three continuous dependent variables to be tested are Percentage of Body Fat Lost or Gained, Weight of Body Fat Lost or Gained, and Total Inches Lost or Gained. The dichotomous independent variables for the three data sets are the invisa-RED Technology Elite Low-level Laser Therapy (LLLT) device and the sham (placebo) device, each administered as therapy in a standardized clinical protocol. The assumptions of normality and homogeneity of variance will be assessed. Normality assumes that the scores are normally distributed (bell-shaped) and will be assessed using the One-Sample Kolmogorov-Smirnov test. Homogeneity of variance assumes that both groups have equal error variances and will be assessed using Levene's Test for the Equality of Error Variances.

Each t-test will be two- tailed with the probability of rejecting the null hypothesis when it is true set at $p < 0.05$. This ensures a 95% certainty that the differences did not occur by chance. *The first t-test* using Data Set One (1) will assess if statistically significant differences exist on the dependent variable Percentage of Body Fat Lost. The second *t-test* conducted on Data Set Two (2) will assess if statistically significant differences exist on the dependent variable Inches Lost. The third *t-test* conducted on Data Set Three (3) will assess if statistically significant differences exist on the dependent variable Weight of Body Fat Lost. For each of the three data sets the independent variables are defined as an Invisia-RED Technology Elite Low-level Laser Therapy (LLLT) device and as a comparator the sham (placebo) device. Data produced by both groups will be a result of a clinical trial governed and conducted by a randomized double-blind study using an approved clinical protocol.

Reference:

Statistics Solutions. (2013). Data analysis plan: Independent Sample t-Test [WWW Document]. Retrieved from <http://www.statisticssolutions.com/academic-solutions/member-resources/member-profile/data-analysis-plan-templates/data-analysis-plan-independent-sample-t-test/>

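### The protocol aims to compare and prove safety against sham, but no safety outcome is defined and no safety comparison by arm is prespecified

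*Protocol*

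**What the plan says.** The Purpose of the Study section of the protocol says the trial will provide data to "compare the efficacy and safety of the invisa-RED Technology Elite Low-level Laser Therapy (LLLT) device with a sham device". Methods and Procedures goes further: "The trial is designed to prove the efficacy and safety of the invisa-RED Technology Elite Low-level Laser Therapy (LLLT) device". Safety is thus one of two declared aims.

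The analysis text is narrower. Purpose of the Study and Methods and Procedures both name change in body fat percentage, weight and inches, and tie them to efficacy. Data Analysis and Data Monitoring says: "The measured weight loss and total inches lost per participant from the two groups will be statistically evaluated". The SAP's Analysis section says: "The three continuous dependent variables to be tested are Percentage of Body Fat Lost or Gained"; the other two are weight of body fat and total inches. The SAP's title begins "Comparing the Efficacy of a Dual-Frequency Laser-Emitting Device", and its three research questions concern the same three measures.

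Four items come close to safety data:

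- Methods and Procedures: "Any medical errors will be included in the statistical analysis".
- Data Analysis and Data Monitoring, having classed the trial as minimal risk and short: "therefore a detailed plan for monitoring the data for participant safety is not required".
- Data Storage and Security: "all clinical records and reports will reference only the participant number".
- Risk/Benefit Assessment: patients are asked about comfort when each session starts and told to report discomfort whenever it occurs.

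**The concern.** If the plan is followed exactly, one of its two aims has no defined outcome and no planned comparison behind it. The protocol itself names what could be counted. Risk/Benefit Assessment says that a mild sunburn-like effect or skin sensitivity may follow if the recommended skin-type settings are not observed, and it discusses the eye hazard of Class 3B lasers. Such events might be noted on paper, but nothing prespecified turns those notes into figures by arm.

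The design makes informal reporting harder to interpret. Staff work with one group exclusively, and the groups attend on different days. Without a common question, a difference in reported discomfort could reflect who asked, and how, rather than the device. At stake is whether a report of this trial can say anything planned about safety against sham.

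**Working it through.** The plan gives no safety figure, event rate or margin, so there is nothing to reproduce. The first step is a reading of both documents; the second asks what the sample could show if events were collected.

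**Step 1: aim against analysis**

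| Place | What is to be analysed | Safety outcome? |
|---|---|---|
| Protocol, Purpose of the Study | Body fat percentage, weight, inches | None |
| Protocol, Methods and Procedures | The same three, plus undefined medical errors | None defined |
| Protocol, Data Analysis and Data Monitoring | Weight, inches | None |
| SAP, Research Questions and Analysis | Percentage of body fat, inches, weight of body fat | None |

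The rows show one absence consistently; they are not four separate defects.

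**Step 2: do the nearby items fill the gap?**

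- *Medical errors.* An error is a process event, and a skin reaction under correct use would be a harm without an error. The two may partly overlap, because the skin effects in Risk/Benefit Assessment are linked to settings not being followed. But no definition, method or comparison by arm is given, and the SAP does not mention the item.
- *Comfort check and instruction to report.* No recording or analysis is stated. The fixed check comes at the start of the session, so no fixed question is planned during or after exposure.
- *Clinical records.* Their content is not described.
- *Monitoring waiver.* It concerns watching data to protect participants. It does not supply an outcome for a stated aim.

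**Step 3: could safety be proven if events were recorded?**

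Inputs: 40 participants projected (Criteria for Participants). The allocation ratio is not stated, so 20 per arm is an assumption.

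Upper limit for the true event rate after 0 events in n = 20:

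- one-sided 95%: 1 − 0.05^(1/20) = 0.139, or 13.9%
- two-sided exact 95%: 1 − 0.025^(1/20) = 0.168, or 16.8%

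These limits describe one arm. For a comparison with sham, take Fisher's exact test at two-sided 0.05 with 20 per arm and no sham events:

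- 4 active events: p = 2 × C(20,4)/C(40,4) = 2 × 4,845/91,390 = 0.106
- 5 active events: p = 2 × C(20,5)/C(40,5) = 2 × 15,504/658,008 = 0.047

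So at least 5 of 20 against 0 of 20 is needed for significance. At assumed true rates of 5% on sham and 20% on active, the power of this test is 17%; about 76 per arm would be needed for 80% power (normal approximation, no continuity correction). The event rates are illustrative, since the documents give none.

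**The case against.** The strongest case on the other side has four parts.

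*The trial is minimal risk and precautions are in place.* Power is set by skin type, eyewear is recommended, and the paddles are placed before activation, which the protocol says removes any chance of direct light entering the eye. This stands as a reason not to ask for a monitoring board or stopping rules, and none is asked for here. It does not give the stated aim an outcome.

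*Medical errors are to be analysed.* The possible overlap with skin effects is conceded. It does not amount to a safety outcome, for the reasons in the working.

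*Harms may be recorded anyway.* Clinical records are kept by participant number, and the user and training manuals, which were not available for this review, may contain recording instructions. A reader might infer that harms will go unrecorded, or that no statement about safety could ever be made. The documents support neither: a post hoc description by arm from paper records could be possible. What is missing is a prespecified comparison, and the SAP text, which runs on without a break, does not contain one.

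*The limits in the working assume data that the plan does not say it will collect.* That is right. They do not measure the gap; they bear only on whether the word prove could be kept after the gap is filled.

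A reader might also infer that skin reactions are expected because pulse and delay are fixed for everyone, whereas Risk/Benefit Assessment says the manual recommends adjusting them, as well as power, for skin type. The protocol says only that such effects may result if the recommendations are not followed, and the manual's values are not shown. This is a reason to count skin reactions, not to predict them.

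**Conclusion.** The point holds as an inconsistency between a stated aim and the plan. Safety is to be compared with sham and proven, but no safety outcome is defined and no comparison of harms by arm is prespecified. As written, no prespecified safety conclusion is possible. The three efficacy tests do not depend on this and are unaffected, and the documents give no ground for saying that participants are unprotected.

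The finding itself rests on the text and needs no numerical assumption. The secondary point, that safety can be described here but not proven, rests on an assumed 20 active participants and the 13.9% and 16.8% limits. The change should be made before the data are analysed, and preferably before treatment starts, since events not asked about cannot be recovered reliably.

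**What to change.** 1. At each of the nine sessions, and at the final measurement if that is a separate contact, ask one identically worded question in both arms about problems during or since the last session. Record skin reaction or sensitivity, discomfort, eye symptoms, any other adverse event, and stopping for discomfort.
2. Add one SAP table: participants with any event, by arm, with exact 95% intervals.
3. In Methods and Procedures replace the aim of proving safety, and in Purpose of the Study the aim of comparing it, with describing safety by arm. The table by arm then matches the aim.
4. If these data will not be collected, delete the safety aim from both sections, which brings the protocol into line with the efficacy-only SAP.

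Cost: one form line, giving 40 × 9 = 360 entries, or 40 × 10 = 400 if the final measurement is a separate contact; one table; and wording in two sections. The downside is a more modest safety claim. No efficacy analysis changes.

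### Safety against sham is a stated aim, but no skin reaction or adverse event is named as recorded or analysed

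*Protocol*

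**What the plan says.** The Protocol makes safety an aim twice. Purpose of the Study says the trial will provide data to "compare the efficacy and safety of the invisa-RED Technology Elite Low-level Laser Therapy (LLLT) device with a sham device". Methods and Procedures goes further: "The trial is designed to prove the efficacy and safety of the invisa-RED Technology Elite Low-level Laser Therapy (LLLT) device".

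The analysis statements are about efficacy. Methods and Procedures says that after nine sessions "the change in body fat percentage, weight, and inches lost of the two groups will be statistically analyzed", and gives determining efficacy as the purpose. Data Analysis and Data Monitoring is narrower: "The measured weight loss and total inches lost per participant from the two groups will be statistically evaluated using an Independent T-Test". The SAP has three research questions, three data sets and three t-tests, on percentage of body fat, inches and weight of body fat.

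Four other statements bear on safety:

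- Methods and Procedures adds: "Any medical errors will be included in the statistical analysis". The term is not defined, and the SAP does not use it.
- Data Analysis and Data Monitoring classes the trial as minimal risk and concludes that "a detailed plan for monitoring the data for participant safety is not required".
- The Risk/Benefit Assessment says that a mild reaction resembling sunburn, or sensitive skin, may follow if the recommended settings for skin type are not observed. Participants are asked about comfort as each session begins and are told to report discomfort whenever it occurs.
- Data Storage and Security says that "only paper records will be maintained for all clinical and personal data". It does not say what the clinical records contain.

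**The concern.** A stated aim needs a variable that answers it. Here one of the two aims has none. The sponsor has already identified the reaction of interest and sets laser power by skin type, but nothing says that a reaction will be written down, graded or counted by arm.

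At the end of the trial the sponsor would have a sham-controlled comparison of body measurements and, at best, scattered clinic notes on tolerability. A statement that the device was shown to be safe would then rest on the absence of recorded events in a trial that had not planned to record them. Notes collected afterwards would be a poor substitute, because no common definition would have applied and, under Methods and Procedures, "staff administering the trial therapy will be assigned to work with one (1) group exclusively". A difference in how staff make notes could not then be told apart from a difference between the devices.

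**Working it through.** **Step 1. Compare the aim with what is analysed.**

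| Place | Variables named for analysis | Safety variable |
|---|---|---|
| Protocol, Purpose of the Study | body fat percentage, weight, inches | none |
| Protocol, Methods and Procedures | body fat percentage, weight, inches; 'medical errors' | none defined |
| Protocol, Data Analysis and Data Monitoring | weight, inches | none |
| SAP, Research Questions and Analysis | body fat percentage, inches, weight of body fat | none |

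The count in the SAP is 3 efficacy variables and 0 safety variables.

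**Step 2. See whether anything else supplies the outcome.**

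- 'Medical errors': an error is an act by staff, while a skin reaction is an effect on a participant. A reaction after a wrong setting might be counted here; a reaction after a correct setting would not obviously be. With no definition, no method and no mention in the SAP, this is not a safety outcome.
- The comfort check: it is a care procedure. Nothing says that the answers are recorded or compared. It is asked as a session begins, so after the ninth session no further check is scheduled.
- The paper records: they may hold reports, but no analysis draws on them.
- The minimal-risk statement: it concerns monitoring while the trial runs. Reporting an outcome at the end is a separate matter.

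**Step 3. What this trial could show if the outcome were added.**

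The documents give no expected reaction rate and no safety calculation, so there is no figure to reproduce.

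Inputs: about 40 participants in two groups (Protocol, Criteria for Participants; SAP, Data Sets/Populations). No allocation ratio is stated, so 20 on the active device is an assumption. I show 15 to 25 as a range.

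With zero events in n people, the exact two-sided 95% upper limit p solves (1 − p)^n = 0.025, so p = 1 − 0.025^(1/n).

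- n = 20: 1 − 0.025^(1/20) = 1 − 0.8316 = 16.8%
- n = 15: 1 − 0.025^(1/15) = 1 − 0.7820 = 21.8%
- n = 25: 1 − 0.025^(1/25) = 1 − 0.8628 = 13.7%

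The chance of seeing at least one event in 20 people is 1 − (1 − r)^20 for a true rate r.

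- r = 5%: 1 − 0.95^20 = 64%
- r = 10%: 1 − 0.90^20 = 88%

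So a clean record would not establish safety, but recording would probably reveal a reaction that affects one person in ten or one in twenty.

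**The case against.** The strongest reply is that the operative plan concerns efficacy only. The SAP's title speaks of comparing efficacy, none of its research questions mentions safety, and both Protocol passages that name safety go on to say that the analysis is there to determine efficacy. On that reading, safety is loose wording in two introductory sentences, and deleting it would remove the mismatch at almost no cost. This largely stands: deletion would make the documents consistent. It would also give up a sham-controlled description of tolerability that can be had at contacts already planned, and as the text stands the aim is explicit.

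A second reply is that the skin reaction is presented as conditional on the settings not being followed, and that exclusions, staff training and the discomfort instruction guard against it. That is correct, and it keeps the point modest. It does not supply an outcome.

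A third is that about 40 people cannot prove safety anyway. That is also correct. It is the reason for asking for a description without a test.

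A reader might go further and infer any of the following. The documents do not support them.

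- *That participants are unprotected, or that the minimal-risk decision was wrong.* The named harm is mild and precautions are described. A detailed monitoring plan is not what is missing.
- *That reactions are expected under correct use.* The Risk/Benefit Assessment ties them to settings that depart from the recommendations.
- *That the fixed pulse and delay breach the device instructions.* The Protocol says that the users manual adjusts these by skin type, but it bases its regimen on the training manual. Neither manual is available here, so this cannot be judged.
- *That the two arms will in fact be noted differently.* Separate staff make this possible; no rate or direction can be given.

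**Conclusion.** The point holds as a gap between aim and plan. Safety against sham is stated as something to be compared and proved, and the plan contains 0 safety variables against 3 efficacy variables in the SAP. Followed as written, the trial cannot answer its safety question. The validity of the efficacy tests is not affected.

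The word prove would be too strong even with an outcome in place. Zero events among 20 active participants would leave a true rate of up to about 17% not excluded (two-sided 95%), or 13.7% to 21.8% for 25 down to 15 participants. That limit rests on an assumed split and on zero events, so it illustrates what the trial can show and is not a fixed property of the design.

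This is a cheap improvement: one of two aims lacks a planned answer, the stated harm is mild, and the remedy uses existing contacts.

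**What to change.** 1. **Protocol, Methods and Procedures.** At each of the nine sessions and at the final measurement, record any skin reaction or other adverse event as present or absent, with a grade. Use one written definition and grading scale for both arms. This keeps the separation of staff by group and gives both teams the same rule.
2. **Protocol, Data Analysis and Data Monitoring, and the SAP.** Add a descriptive table: number and proportion of participants with any event, by arm, with exact two-sided 95% confidence intervals and no significance test.
3. **Medical errors.** Define the term and report these errors separately from adverse events.
4. **Protocol, Purpose of the Study and Methods and Procedures.** Say that the trial describes safety rather than proves it. Note that with about 20 active participants (1:1 assumed), zero events would leave a true rate of up to about 17% not excluded.

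The cost is at most 40 × 9 = 360 session entries plus 40 final entries, 400 short entries in all, with no added participants or visits. The documents do not describe a session form, so one may have to be drawn up. Asking at every session may raise the number of mild reports in both arms, and the sponsor ends with a weaker safety statement.
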